Study Protocol and Statistical Analysis Plan

Official Title: Novel Management of Airway Protection in Parkinson's disease: A clinical trial

NCT number: NCT02927691

Document Date: (Grant submission – February 2016)

Study Protocol

This prospective experimental study will include two participant groups; one group will receive EMST and the other smTAP. Briefly, once enrolled in the study, participants will undergo baseline testing consisting of airway protective measures, physiological measures of respiratory and laryngeal function, and patient-centered outcome measures. Participants will then be randomly assigned with allocation concealment to either the EMST or smTAP training groups. They will be further randomized to receive immediate training or delayed training where there is a 5-week wait to start with a second baseline performed at the end of the 5-week delay. Whether participants are in the immediate or delayed start groups, once treatment commences they will receive 5 weeks of intensive training including weekly meetings with a treating clinician in our clinical-research laboratory. Upon completion of the treatment arm, participants will return for a post-treatment assessment consisting of all tests and measures from the initial baseline assessment. All treatment and assessment visits will be completed 'on' optimal PD medication dosage which will be defined as one hour after medication administration. Participants may use diet and/or postural modifications as recommended by their treating Speech-Language Pathologist to maintain nutritional status and swallowing safety during enrollment in the study, but are not to participate in other dysphagia exercise-based rehabilitation including treatments such as the effortful swallow, mendelsohn maneuver, etc. that have been shown to have exercise training effects (e.g., [10]). Pre- and post-treatment procedures are described below. More specific information about the selected outcomes is included in the 'clinical protocol synopsis'.

Pre and Post Treatment Assessments

Swallowing Assessment Procedures. Three 10 cc thin liquid boluses by spoon and three 3-oz thin liquid sequential swallow challenges will be administered by cup. Our research team has extensive experience in the evaluation and measurement of swallowing dysfunction in PD (e.g., [20, 30, 31]). A recent retrospective analysis by our group of the swallowing performance of 50 participants with PD demonstrated that the 3-oz sequential swallow presentation was the best bolus presentation to detect change in swallowing performance. We will also include a smaller bolus (10 cc.) in the case that swallowing performance is so severe that it precludes the ethical presentation of the 3-oz liquid challenge.

Reflex Cough Assessment Procedures. Participants will be outfitted with a facemask covering the nose and mouth. The facemask will be coupled to a pneumotachograph, differential pressure transducer, and have a side port with a one-way inspiratory valve for nebulizer connection. The nebulizer will be a DeVilbuss T-piece connected to a dosimeter that delivers aerosolized solution during inspiration with a delivery duration of two seconds. The cough airflow signal will be digitized (Power Lab Data Acquisition System) and recorded (LabChart 7; ADInstruments, Inc) to a laptop computer.

Participants will be seated for an initial 30 seconds of quiet breathing in order to acclimate to the facemask. Participants will then complete a capsaicin challenge with three randomized blocks of 0, 50, 100, 200, and 500 μ M capsaicin dissolved in a vehicle solution. Our preliminary data identified 500 μ M as a supra-threshold concentration for eliciting the reflex cough in participants with PD. Participants will be given the instruction "cough if you need to" prior to capsaicin delivery. The solution will be administered automatically upon detection of an inspired breath and there will be a minimum of one minute between each trial. Participants will be provided water to drink between trials. Our research group has extensive experience utilizing this methodology to induce cough (e.g., [8, 22, 32, 33]). Our group holds an FDA IND # 76866 for the use of capsaicin in the study of cough reflex sensitivity and motor pattern.

Treatment protocols:

Every effort was made to match the two targeted treatments on amount of time with clinicians, home practice time, and number of repetitions.

Expiratory Muscle Strength Training (EMST)

EMST involves a calibrated device consisting of a mouthpiece with a one-way spring-loaded valve. The valve blocks airflow until a sufficient "threshold" pressure is produced to overcome the force. The pressure range is from 25 cm H_20 to 150 cm H_20 . Participants will receive training at baseline, have the device set to 75% of his/her MEP, and then complete EMST five days per week for five weeks. During that time period they will be seen for weekly study-treatment visits in our clinicalresearch laboratory which will last approximately 45 minutes.

Weekly study-treatment visits:

During weekly visits, a study clinician will re-measure MEP, re-set the EMST device as appropriate (75% MEP), and observe the participant complete the targeted 25 repetitions. MEPs are completed by having the participants blow into a mouthpiece connected to a pressure manometer via tubing with a 14-guage needle air-leak. The participant blows into the manometer for two seconds.

Home practice:

The daily training sessions will be completed at home, with the assistance of the participant's primary caregiver if necessary. Each day approximately 20-30 minutes will be spent training. The daily training is identical to the protocol described above.

Sensorimotor Training for Airway Protection (smTAP)

Participants will complete 45 minutes of cough rehabilitation in the laboratory with a trained research clinician once a week for five weeks. During the weekly visits, participants will complete 25 'hard/long coughs' at sub-threshold levels of capsaicin. Level of capsaicin will be determined from baseline (pre-test) measures. Participants will train at the concentration just preceding their reflex cough threshold (C2). Attentional focus to the sub-threshold stimulus will be emphasized. Visual feedback will be provided in real time via LabChart 7 (ADInstruments, Inc) and will be displayed on a large 20 inch desktop computer monitor. A visual target line 25% above maximum PEFR (derived from baseline cough assessment; figure 5) will be provided during cough training in order to promote enhanced PEFR. PEFR was selected as a primary target given that it has been identified as a measure which can be modified through cueing of reflex cough [22], is related to swallowing outcomes [34, 35], can be visually targeted by participants, and is associated with increased cough effectiveness. The participants will only be provided with feedback regarding

their performance on the first five coughs trained within each session in order to reduce the influence of clinician bias on treatment outcomes.

Home practice: The daily training sessions will be completed at home, with the assistance of the participant's primary caregiver if necessary. Each day approximately 20-30 minutes will be spent training. Home practice will be completed 5 out of 7 days. Participants will complete 25 voluntary coughs (5 sets of 5 repetitions) using a peak flow meter [36]. Each week the target peak cough flow will be 25% above maximum PEFR as identified during the study treatment visits to the laboratory.

Statistical Analyses

Multilevel models with main effects of treatment, time, and their two-way interaction will be used. A randomeffect of participant will be used to include multiple trials (eg, three trials of MEP at each time point). In the presence of an interaction, differences in the magnitude of change between groups, as well as changes within each group, will be examined. For primary outcomes, separate models will be performed for delayed to pre-training and pre-training to post-training cohorts. More specifically, for participants randomized to the delayed treatment group, MEP and voluntary cough PEFR will be tested between delayed (first baseline) and pre-training (second baseline). For the active treatment phase, all outcomes will be tested between pre-training. α will be set at 0.05, and multiple pairwise comparisons were adjusted via Holm–Bonferroni corrections. Standardized effect sizes will be computed by dividing mean difference by the error and random effect variance. Single measure, absolute agreement intraclass correlation coefficients and weighted Cohen's kappa will be used for cough airflow and number of coughs, respectively, for reliability. Analyses will be performed in R.

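### Delayed starters are assigned to EMST or smTAP before the 5-week wait, so their pre-training value and any waiting-period dropout follow arm assignment, and nothing says the arm is withheld until then.

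*Combined protocol and SAP*

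**What the plan says.** The Study Protocol section gives the order of events. First, "once enrolled in the study, participants will undergo baseline testing consisting of airway protective measures". Next, "Participants will then be randomly assigned with allocation concealment to either the EMST or smTAP training groups". Then comes start time: "They will be further randomized to receive immediate training or delayed training where there is a 5-week wait to start with a second baseline", which is "performed at the end of the 5-week delay".

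Statistical Analyses splits the follow-up into two periods: "separate models will be performed for delayed to pre-training and pre-training to post-training cohorts". For the waiting period in the delayed group, "MEP and voluntary cough PEFR will be tested between delayed (first baseline) and pre-training (second baseline". So the pre-training value of a delayed starter is the second baseline. For training itself, "For the active treatment phase, all outcomes will be tested between pre-training"; that sentence breaks off, and the other end is evidently post-training, since the preceding text names that interval. The arm comparison is the interaction of treatment with time. The model has no term for start group and none for the first baseline.

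The only protection mentioned is allocation concealment. The documents do not say when a participant or tester learns the arm, whether testers are masked at either baseline, how waiting-period losses are handled, or which participants form the analysis population.

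**The concern.** A change score compares arms fairly when its starting value cannot have been influenced by the arm. That is secure for immediate starters, whose pre-training value is taken before assignment. For delayed starters it is taken 5 weeks after.

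MEP and voluntary cough PEFR depend on effort, and each resembles the task of one arm: MEP is a forced blow, as in EMST, and PEFR is what smTAP trains. A participant who knows the arm may try out the task, hold back, or approach the second test differently, and a tester who knows it may coach differently. The authors recognise this kind of influence: the smTAP section restricts feedback within sessions in order to limit clinician bias. No equivalent protection is described for the second baseline.

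Dropout is the second route. A delayed starter who leaves during the wait has neither a pre-training nor a post-training value, and so contributes nothing to the active-phase comparison. If the reason is tied to a known arm, the arms being compared are no longer those that were randomised.

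**Working it through.** The plan states no sample size, allocation ratio, SD, effect size or dropout rate, so there is no figure to reproduce. The check is first of sequence, then of the form that a bias would take.

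**Sequence**

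| Step | Immediate start | Delayed start |
|---|---|---|
| First baseline | before arm assignment | before arm assignment |
| EMST or smTAP assigned | yes | yes |
| Start time assigned | yes | yes |
| 5-week wait | none | after arm assignment |
| Pre-training value used in the arm comparison | first baseline, **before** assignment | second baseline, **after** assignment |

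If both randomisations happen at one visit, both still precede the wait and the table does not change.

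**Form of a measurement bias**

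Assume that immediate and delayed starters are pooled in the active-phase model, as the absence of a start-group term implies, and that the delayed share is the same in both arms. Let
- q = share of participants with delayed start;
- s = shift in the second baseline caused by knowing the arm, EMST minus smTAP;
- c = fraction of that shift still present at post-training, from 0 to 1.

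A higher second baseline lowers the measured change, except for the part that persists. Hence

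bias in the EMST-minus-smTAP difference in change = −q × s × (1 − c).

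All three inputs are unknown. For illustration only, with s in SD units:
- q = 0.5, s = 0.2, c = 0: size 0.5 × 0.2 × 1 = 0.10 SD.
- The same with c = 0.5: 0.5 × 0.2 × 0.5 = 0.05 SD.
- The same with c = 1: 0.
- c = 0 over a wide grid: from 0.33 × 0.1 = 0.033 SD to 0.67 × 0.5 = 0.335 SD.

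If the arm is unknown during the wait, s = 0 and the bias is 0 for every q and c. Sample size does not appear in the formula, so recruiting more participants would not reduce the bias.

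**Form of a dropout bias**

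Loss during the wait biases the comparison only if it differs by arm, in amount or in kind, and is related to the change that the lost participants would have shown. A loss rate alone is not a bias. The documents give no information on either condition.

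**Does the planned waiting-period model deal with it?**

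Read with the general model statement, it would include treatment-by-time, and that term estimates s. But it covers only the delayed subset and only MEP and voluntary cough PEFR, whereas the active phase tests all outcomes. Its result is not fed into the active-phase model, and a non-significant result would not exclude a shift.

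**The case against.** The strongest reply is that the order of randomisation is harmless in itself. Every measurement route needs the participant or tester to know the arm during the wait. The documents say when the arm is assigned, in a paragraph introduced as a brief summary, but never when it is revealed. That the trainings cannot be disguised once begun does not show that the arm is known in 5 weeks without training. This stands, and it makes the concern conditional. It does not close it: allocation concealment protects the act of assignment, not a measurement 5 weeks later, and one sentence stating that the arm stays sealed would settle the measurement part. That sentence is absent.

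It is also fair that immediate starters dilute any bias, that the waiting-period model would give some sight of a shift in two outcomes, and that the missing analysis population and missing-data method are a wider gap than waiting-period dropout. None of these removes the problem.

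A reader might go further and infer that EMST training begins inside the wait, because the EMST section says "Participants will receive training at baseline, have the device set to 75% of his/her MEP". The documents do not support that. The same sentence runs straight on into the five training weeks, the Study Protocol section describes the delay as a wait before starting, and the smTAP section equates baseline with the pre-test. Read together, baseline here is the pre-training assessment. At most the wording needs aligning.

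**Conclusion.** The point holds as a conditional weakness that is cheap to remove. The sequence is explicit: for delayed starters, the starting value of the arm comparison and any waiting-period loss come after arm assignment. Whether bias follows depends on the arm being known to participants or testers during the wait, and on effort, testing or dropout then differing by arm. The documents neither state nor exclude this.

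It would be wrong to conclude that the comparison is biased, or to attach a clinical size to the bias in units of MEP or PEFR. The delayed share, the shift, its persistence and the loss rate are all unknown. The SD figures above show only how a bias would scale, under pooled analysis and equal delayed shares in the two arms.

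**What to change.** Reverse the two randomisations. At the first baseline, randomise start time only. Draw the EMST or smTAP assignment, stratified by start group, once the pre-training assessment is complete: after the first baseline for immediate starters and after the second baseline for delayed starters. Every pre-training value then precedes the arm, and waiting-period losses fall before arm assignment.

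At minimum, if the present order is kept, state that the assignment stays sealed from participants and staff until the second baseline is finished, and report waiting-period losses by arm.

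Two consequential edits follow. With the arm drawn later, the waiting-period model becomes a test of time alone, because no arm exists yet. The EMST section's reference to baseline should name the pre-training assessment.

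The cost is protocol wording and a reordered randomisation list, with no extra visits, staff or participants. The one drawback is that delayed participants learn their training type 5 weeks later. The change does not mask the post-training assessment, which is a separate matter.

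### The only post-training assessment is scheduled on completing treatment, with no planned assessment of early stoppers, so the pre-to-post comparison rests in effect on completers.

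*Combined protocol and SAP*

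**What the plan says.** The Study Protocol section fixes the length of training for both arms: "once treatment commences they will receive 5 weeks of intensive training including weekly meetings with a treating clinician in our clinical-research laboratory". The next sentence sets the follow-up measurement, which repeats the whole baseline battery: "Upon completion of the treatment arm, participants will return for a post-treatment assessment". No calendar time or visit window is given, and nothing is said about a participant who stops before the fifth week.

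The Statistical Analyses section plans multilevel models with treatment, time and their interaction, and says that for the primary outcomes "separate models will be performed for delayed to pre-training and pre-training to post-training cohorts". The participant random effect is introduced to accommodate repeated trials at a time point, not dropout. The section states no analysis set, no intention-to-treat principle and no missing-data method.

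On burden, the Treatment protocols section says "Every effort was made to match the two targeted treatments on amount of time with clinicians, home practice time, and number of repetitions". On measurements during training, the EMST weekly-visit text says "During weekly visits, a study clinician will re-measure MEP". The smTAP home-practice text sets each week's target from the maximum PEFR found at the laboratory visits.

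**The concern.** Completing training is an event after randomisation. If the only outcome measurement depends on it, the people measured are selected by how training went. Those who tolerate training poorly or make no progress may be under-represented at the post-training visit, which would overstate the change in each arm. If that selection differs between arms, it would also distort the EMST-versus-smTAP difference.

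The two arms ask for different things. smTAP visits involve repeated hard coughing with sub-threshold capsaicin; EMST involves blowing against a threshold set at 75% of MEP. Reasons for stopping could therefore differ. A post-training value that was never collected cannot be recovered at the analysis stage.

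**Working it through.** The plan gives no stopping rate, SD, effect size or sample size, so there is no figure of its own to reproduce. Three checks were made.

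**1. Is the planned burden unequal?** From the Treatment protocols section, the inputs are the same in both arms: five weekly visits of about 45 minutes, home practice of 20–30 minutes a day, five training days a week, and 25 repetitions a session.

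- Clinic time: 5 × 45 = 225 minutes in each arm.
- Home practice: 25 days × 20–30 minutes = 500–750 minutes in each arm (20 days, 400–600 minutes, if the visit counts as one of the five days).
- Repetitions: 25 × 5 × 5 = 625 in each arm, or 25 × 6 × 5 = 750 if the visit is extra.
- Training coughs with capsaicin: 5 × 25 = 125 in smTAP, none in EMST.

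The amounts are equal; the arms differ in kind.

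**2. What does an early stopper contribute to the model?** The active-phase comparison runs from pre-training to post-training. (The sentence on the active phase breaks off before its end point, but an earlier one names post-training.) With two time points, a participant with only a pre-training value can be kept in a likelihood-based fit but adds almost nothing to the estimated change. The estimate is protected if stopping is unrelated to outcome, or depends only on what the model observes, chiefly arm and pre-training value. It is not protected if stopping depends on how training is going.

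**3. How large could the bias be?** Assume that change is normal, that a fraction *d* stops, and that stopping is governed by a threshold on a normal variable correlated ρ with change. The completer mean then exceeds the mean of everyone who started training by

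ρ × φ(z_d) / (1 − d), in SD of change.

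Both *d* and ρ are assumptions.

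| d | φ(z_d) | φ(z_d)/(1 − d) | ρ = 0.3 | ρ = 0.5 |
|---|---|---|---|---|
| 5% | 0.103 | 0.109 | 0.03 | 0.05 |
| 15% | 0.233 | 0.274 | 0.08 | 0.14 |
| 25% | 0.318 | 0.424 | 0.13 | 0.21 |

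Between-arm bias, with the same ρ in both arms:

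- Equal rates: about 0.
- 15% versus 5%: (0.274 − 0.109) × 0.3 to 0.5 = 0.05 to 0.08 SD.
- 25% versus 5%: (0.424 − 0.109) × 0.3 to 0.5 = 0.09 to 0.16 SD.

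A simpler form gives the same order of size. If completers and stoppers differ by *g* SD, the completer mean is off by *d* × *g*, and the between-arm bias is d₁g₁ − d₀g₀. At 20% versus 10% with *g* = 0.5 in both arms it is 0.10 − 0.05 = 0.05 SD. At 20% in both arms with *g* = 0.5 in one and 0 in the other it is 0.10 SD, so equal rates alone do not guarantee a fair comparison. With *g* = 0 it is zero whatever the rates.

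**The case against.** The strongest reply is that the text is silent on early stoppers rather than prohibitive. The sentence belongs to a brief overview, follows directly on a stated five-week duration, and could be read as meaning the end of that phase for everyone. This stands as a point of wording: a reader might infer that early stoppers are barred from assessment, and the documents do not say so. But they do not provide for it either. The clinical protocol synopsis, which is not among the documents here, is cited for detail on outcomes, not follow-up.

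A reader might also infer that the arms carry very different burdens. The matching statement and the equal minutes, days and repetitions contradict that. The capsaicin argument is weaker than it first looks, because smTAP trains at sub-threshold levels and every participant meets concentrations up to 500 μM at baseline, before assignment. What remains is that repeated exposure during training occurs only in smTAP. Whether this leads to unequal stopping is unknown.

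Nor is interim measurement confined to EMST: MEP is taken weekly there, and PEFR is obtained at smTAP visits. Each arm thus has interim data on its own training target. The two cover different outcomes, so they cannot stand in for a common post-test.

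Finally, the bias figures rest wholly on assumed rates and correlations. That is true, and they are offered only as a range.

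**Conclusion.** The gap is real. As written, the plan has one post-training measurement, tied to completion, with no planned assessment of early stoppers, no analysis set and no missing-data handling. Within-arm changes and the between-arm comparison therefore rest in effect on completers.

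The consequence is conditional and modest. Bias requires stopping that is related to how training goes; between-arm bias also requires a difference in rate or selectivity. Under the assumed correlations and rates of 5% to 25%, it runs from about zero to 0.16 SD of change between arms. The within-arm overstatement does not vanish when rates are equal, and it matters because the plan examines change inside each arm when there is an interaction. The direction of any between-arm bias is not known: it favours the arm with more stopping only if poor responders stop equally selectively in both.

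It might be inferred that the randomised comparison is lost. Neither the documents, which give no stopping data, nor these figures support that; the comparison is exposed to an avoidable risk.

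**What to change.** In the Study Protocol section, state that all randomised participants who start training return for the post-treatment assessment at the end of the planned five-week training period, whether or not they completed it, unless they withdraw consent to assessment. Give a visit window wide enough for delayed sessions; without one, a participant whose visits slip could be tested before finishing training.

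In the Statistical Analyses section, state that these values enter the pre-to-post model in the randomised arm, and add a completers-only analysis as a sensitivity analysis.

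The cost is one protocol sentence, one analysis sentence, and an already-planned visit for those who stop early. The estimated training effect may be somewhat smaller, because it then describes everyone who started training, not only those who finished. That is a choice of what to estimate, and the plan should make it openly.

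### MEP and PEFR: the EMST-versus-smTAP contrast uses the pre-training value only by subtraction; adjusting for it could give a modest gain in precision at low cost

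*Combined protocol and SAP*

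**What the plan says.** The Statistical Analyses section specifies "Multilevel models with main effects of treatment, time, and their two-way interaction will be used". On repeated trials it adds: "A randomeffect of participant will be used to include multiple trials (eg, three trials of MEP at each time point". For primary outcomes, "separate models will be performed for delayed to pre-training and pre-training to post-training cohorts". If the interaction is present, the plan examines "differences in the magnitude of change between groups" and the change within each group. The sentence on the active phase breaks off after naming the first of its two visits. I read it as pre- to post-training, in line with the sentences before it.

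No baseline covariate and no common pre-training mean is mentioned anywhere. A treatment main effect is included, so pre-training means are free to differ by arm.

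The Study Protocol section gives the design: "Participants will then be randomly assigned with allocation concealment to either the EMST or smTAP training groups". The ratio is not stated. Delayed starters have "a 5-week wait to start with a second baseline performed at the end of the 5-week delay", so their pre-training value is taken after randomisation but before training. At the end, "participants will return for a post-treatment assessment consisting of all tests and measures from the initial baseline assessment". The document gives no sample size, SD, pre-post correlation or power.

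**The concern.** With complete data, the arm-by-visit term in this model is the difference between arms in mean post-minus-pre change. This applies a slope of exactly 1 to the pre-training value, whatever the data show. A regression or a common-mean longitudinal model estimates that slope instead and, in a randomised comparison, usually gives a more precise estimate of the same difference.

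At stake is the precision of the trial's randomised comparison. The measurement is already scheduled, so better use of it needs no extra visit or test.

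**Working it through.** There is no figure in the plan to reproduce. The comparison below is of true sampling variances, with inputs that are assumptions because the document gives none:

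- ρ: pre-post correlation of participants' visit means, 0.5 to 0.9
- k: post-training SD divided by pre-training SD, 1 or 1.25
- N: total participants, 20, 40 or large
- allocation 1:1

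**Formulas**, per unit of pre-training variance (both share the same factor for arm sizes):

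- change contrast: 1 + k² − 2kρ
- adjusted contrast: k²(1 − ρ²)
- gap: 1 + k² − 2kρ − k² + k²ρ² = (1 − kρ)², never negative, and zero only when the post-on-pre slope kρ equals 1

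Estimating the slope multiplies the adjusted variance by about (N − 3)/(N − 4): 37/36 = 1.028 at N = 40 and 17/16 = 1.0625 at N = 20.

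**Ratio of adjusted to change variance**

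| k | ρ | Change | Adjusted | Large N | N = 40 | N = 20 |
|---|---|---|---|---|---|---|
| 1 | 0.5 | 1.00 | 0.75 | 0.750 | 0.771 | 0.797 |
| 1 | 0.7 | 0.60 | 0.51 | 0.850 | 0.874 | 0.903 |
| 1 | 0.8 | 0.40 | 0.36 | 0.900 | 0.925 | 0.956 |
| 1 | 0.9 | 0.20 | 0.19 | 0.950 | 0.976 | 1.009 |
| 1.25 | 0.5 | 1.3125 | 1.1719 | 0.893 | 0.918 | 0.949 |
| 1.25 | 0.7 | 0.8125 | 0.7969 | 0.981 | 1.008 | 1.042 |
| 1.25 | 0.8 | 0.5625 | 0.5625 | 1.000 | 1.028 | 1.0625 |
| 1.25 | 0.9 | 0.3125 | 0.2969 | 0.950 | 0.976 | 1.009 |

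With k = 1 and large N the ratio is (1 + ρ)/2. Its square roots are 0.866, 0.922, 0.949 and 0.975, so the CI narrows by about 13%, 8%, 5% and 2.5%. As an illustration, if the change contrast had 80% power at two-sided 0.05, the adjusted one would have about 90%, 86%, 84% and 82%.

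**Simulation check** (three trials per visit, k = 1, ρ = 0.7): the ratio was 0.850 with 100 per arm, against 0.850 in theory. With 30 per arm it was 0.869, against 0.850 × 57/56 = 0.865.

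**Allocation.** In a simulated 25:75 split, with slope 1.0 in the smaller arm and 0.5 in the larger, adjustment with a single slope had 1.29 times the variance of change. Adding a baseline-by-arm term brought this to 0.89. With the same two slopes and 1:1 arms, single-slope adjustment gave 0.72.

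**Covariance form.** A common-mean model that forces equal variance at both visits uses the slope 2kρ/(1 + k²). At k = 1.25 and ρ = 0.8 this is 2/2.5625 = 0.780. The variance is then 1.5625 − 2(0.780)(1.0) + 0.780² ≈ 0.611, against 0.5625 for change, a ratio of 1.086.

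**The case against.** **The plan already uses the baseline.** A reader might infer that the pre-training value is ignored. It is not: each participant's own value is subtracted. With k = 1, and relative to comparing post-training values alone, the change contrast has variance 2(1 − ρ) and the adjusted one 1 − ρ². At ρ = 0.7, 0.8 and 0.9 the plan removes 40%, 60% and 80% of the variance, against 49%, 64% and 81% after adjustment. That is about 82%, 94% and 99% of what can be had. Only at ρ of 0.5 or below does subtraction gain nothing. This stands, and it limits the size of the point.

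**The gain may be nil here.** Training is scaled to the individual. EMST participants "have the device set to 75% of his/her MEP", and smTAP targets are set from the participant's own peak flow. This could move the post-on-pre slope either way. At k = 1.25 and N = 40, two of the four correlations in the table show a small loss. This also stands.

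**Adjustment brings an assumption.** A reader might infer that adjusting can never hurt. It needs 1:1 allocation or a baseline-by-arm term, and enough participants. For delayed starters it also needs the wait to be unrelated to assigned arm. The planned contrast leaves pre-training means free, so it still estimates the difference in change over training if that fails. This is a real cost.

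**Printed intervals are a separate matter.** If the participant effect is an intercept only (not stated), the planned model's printed CI can be too narrow. In one simulated case (N = 40, ρ = 0.7, three trials per visit, participant-by-visit variance 0.2 and trial variance 0.3 on a scale where visit-mean variance is 1), the mean width was 0.655 printed, 0.985 from participant-level changes and 0.921 adjusted. A covariate is not the remedy for that, and it is not evidence for this point. It does mean that the two analyses must not be compared on printed width.

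**Conclusion.** The point holds as a matter of precision and is worth considering. The planned contrast is valid, and nothing in the document supports reading it as biased by chance baseline imbalance. The subtraction simply fixes at 1 a slope that could be estimated.

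Under 1:1 allocation and large samples, the adjusted contrast is at least as precise, and strictly more so unless the slope is 1. With equal SDs, the plausible range is a 5% to 25% saving in variance. In the cases tabulated for N = 20, the result runs from about a 20% saving to about a 6% loss. All sizes rest on assumed ρ, k, N and allocation, so the document cannot show how much this trial would gain. My confidence in the size is only moderate.

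**What to change.** For continuous outcomes such as MEP and PEFR, prespecify the baseline-adjusted EMST-minus-smTAP difference with its 95% CI, in one of two forms:

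- **(a) Preferred.** Fit a longitudinal model to visit means with a common pre-training mean for both arms and an unstructured covariance. Its treatment-by-time term is the adjusted difference, so the planned interaction test, its order and the within-group changes can stay, and participants with only one visit contribute. The unstructured form avoids the loss from forcing equal variances.
- **(b) Alternative.** Regress the post-training mean on arm and the pre-training mean, adding a centred baseline-by-arm term if allocation is not 1:1. This needs a separate model for within-group changes and drops anyone missing either visit.

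For delayed starters use the second baseline. State the assumption that change and dropout during the 5-week wait do not differ by assigned arm, because that value follows randomisation.

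The cost is SAP wording, one degree of freedom (one more with the interaction term), a possible slight loss of precision in a very small trial, and that assumption.
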